5.4 SCREEN FAILURES

Screen failures are defined as participants who consent to participate in the clinical trial but are not subsequently randomly assigned to the study intervention or entered in the study. A minimal set of screen failure information is required to ensure transparent reporting of screen failure participants, to meet the Consolidated Standards of Reporting Trials (CONSORT) publishing requirements and to respond to queries from regulatory authorities. Minimal information includes demography, screen failure details, eligibility criteria, and any serious adverse event (SAE).

Individuals who do not meet the criteria for participation in this trial (screen failure) because of use of prohibited medications that have subsequently been discontinued may be rescreened. Rescreened participants should be assigned the same participant number as for the initial screening.

5.5 STRATEGIES FOR RECRUITMENT AND RETENTION

Potential subjects who are interested in elective mini-facelift surgery will be recruited through IRBapproved flyers on bulletin boards, physician referrals, websites (SUNY Downstate Department of Dermatology webpage, SUNY Downstate Clinical and Translational Science Center "Clinical Trials List", StudyPages.com, and ClinicalTrials.gov), social media, website ads, radio ads, and/or newspaper ads. Potential participants will be identified by their expressed interest in a mini-facelift or perceived suitability for the surgery (i.e., they have excess lax facial skin and desire a mini-facelift). Aside from physician referrals and direct recruitment from clinic, recruitment materials will be distributed or made available to the general public. That is, potential participants may learn about the study and approach or contact the research team directly. We anticipate screening up to 150 potential participants and ultimately enrolling 30 subjects.

At the initial screening visit, investigators will explain the study, provide relevant literature and information, and answer all questions. Written informed consent will be obtained prior to any study-related procedures or interventions. We will indicate that the subjects will receive the same standard of clinical care options regardless of whether they decide to participate in the study. Subjects will be informed that the costs of the surgery are covered by the research study and that participation is voluntary, allowing them to withdraw from the study at any time.

Measures to minimize undue influence: Due to the nature of this research study, specifically the provision of an elective cosmetic procedure at no cost to the subject, measures are in place to minimize undue influence. The fact that the cost of the surgery is covered by the Department of Dermatology will not be advertised in recruitment materials. That is, we are not emphasizing "free surgery" as a way to gain the attention of potential subjects. In the recruitment materials, we call for volunteers who are considering or interested in a mini-facelift, without commenting on whether the surgery itself is part of the study. The fact that the surgery will be provided at no cost for enrolled subjects is disclosed during the informed consent process (i.e., after a potential subject makes contact with the research team to express interest in the study and comes in-person for the screening visit). With this recruitment strategy, we will be able to screen potential subjects who are already aesthetically motivated and inclined to undergo cosmetic surgery such as a mini-facelift, regardless of the opportunity provided by this study. During the informed consent process, the individual's comprehension of risks, benefits, and outcome expectations are of paramount concern when determining appropriate candidates for the mini-facelift. In this study, there is an ethical concern that an offer of no-cost surgery may impair an individual's judgment such that they do not fully consider risks and thus engage in activities that contravene their interests. To minimize this risk, we will conduct an assessment of the individual's understanding and appreciation of the surgery's risks/benefits and alternative options to ensure that they demonstrate decision-making capacity. We will emphasize that research participation is voluntary, that the subject can withdraw at any time, and that the decision whether or not to participate will have no impact on the availability of care. Known benefits of the mini-facelift and the study intervention will be stated accurately but not exaggerated; potential or uncertain benefits will also be stated as such, with clear language indicating how much is known about the uncertainty or likelihood of these potential benefits. For example, we will ensure that the potential subject has reasonable expectations about the cosmetic outcome of the minifacelift; they should understand what the mini-facelift can and cannot do to change physical appearance. We will seek consent only under circumstances that provide the prospective subject sufficient opportunity to consider participation and that minimize the possibility of undue influence.

To minimize potential for drop-out due to scheduling conflicts, subjects will be directly asked prior to enrollment if they are willing and able to be compliant with therapy (i.e., be able to attend all proposed study visits on the schedule). We will educate subjects regarding the benefits and risks of the study, as well as importance of attending all treatment sessions and follow-up visits for subject safety. We will guard against drop out by confirming study visits with subjects in advance to ensure no scheduling conflicts via multiple methods of communication including phone calls, email, and text message reminders. To minimize subject burden and enhance retention, we will make every attempt to accommodate subject preferences in scheduling time (e.g., treatment sessions in the mornings only). All treatment sessions and follow-up visits will be in the same location.

We hypothesize that drop-out will be low, as we hope that subjects are interested in and motivated to limit post-surgical scarring for functional and aesthetic reasons.

Subjects will be compensated for study participation. A total amount of \$375 will be given in the form of gift cards and/or checks. Subjects will receive \$100 at the end of each week during the 3-week treatment period, plus \$25 for each of the 3 follow-up visits. In the event that a subject withdraws early from the study, the payment will be prorated based on the number of study visits completed prior to withdrawal.

6 STUDY INTERVENTION

6.1 STUDY INTERVENTION(S) ADMINISTRATION

6.1.1 STUDY INTERVENTION DESCRIPTION

The LED light source is the Omnilux new-U handheld LED phototherapy device, which is commercially available and FDA-cleared for the treatment of periorbital wrinkles. This device has not been approved or cleared for the indications the protocol is designed to investigate (skin fibrosis). The device has a 3-position switch that allows the user to select the red light output (switch down).

The mock therapy device emits no irradiation. The mock therapy device has a ventilation fan and functional resistors designed to sound, look, and feel (i.e., temperature matched) similar to the phototherapy treatment device, but does not emit LED-RL.

6.1.2 DOSING AND ADMINISTRATION

Randomization:

A computer-based randomization algorithm will be used to assign subjects to three different treatment groups to receive LED-RL at the following doses: 160 J/cm², 320 J/cm², or 480 J/cm². The treatment side (right face versus left face) will also be randomized using the same algorithm. The same dose will be maintained throughout all treatment sessions for each individual subject, with no dose escalation. Refer to *Section 6.3: Measures to Minimize Bias* for a detailed description of the randomization protocol.

Treatment Protocol:

The subject will be inside a private clinic examination room. The subject's periauricular skin on both sides of the face will be cleaned with alcohol pads. A surgical marking pen will be used to outline the treatment area at the start and completion of every treatment. The Omnilux new-U device and mock therapy device will be aimed at the periauricular skin and positioned in close contact with the skin (maximum of 1 cm from the skin surface), held in place by a hair net throughout the duration of the treatment. LED-RL phototherapy and mock therapy are administered simultaneously. Subjects will be allowed to receive the treatment sitting up or laying down, per personal preference for a comfortable position.

Duration of the treatment administration for each group is as follows:

- Group 1: LED-RL 160 J/cm² and mock therapy 30 minutes
- Group 2: LED-RL 320 J/cm² and mock therapy 60 minutes
- Group 3: LED-RL 480 J/cm² and mock therapy 90 minutes

[name] (research coordinator) will perform the phototherapy, observe the treatment session, and assess for any safety issues that may arise. Any adverse events reported by the subject or observed by the investigator will be recorded. Common expected post-treatment effects include mild erythema, warmth, and swelling, which are expected to resolve within 24 hours.

Subjects will receive LED-RL phototherapy and mock therapy sessions in-office three times weekly, starting at approximately 1 week post-surgery, for a total of nine treatment sessions. The duration of treatment administration is controlled by the investigator (i.e., the investigator will take responsibility for timing the treatment and determining when the devices are turned off to end treatment).

The Omnilux new-U has been tested to international standards to ensure that its outputs are safe for the eyes. However, subjects will wear safety goggles during the treatment sessions, as recommended by the manufacturer for patient comfort.

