Description of Study Intervention:	The LED-RL source is the Omnilux new-U handheld phototherapy device (GlobalMed Technologies, Glen Ellen, CA), which is commercially available over-the-counter and FDA-cleared for the treatment of periorbital rhytides. The device has a 4.7 cm x 6.1 cm rectangular aperture of LED arrays and emits visible red light (633 nm \pm 6 nm) at a power density of 360.2 W/m ² at room temperature. Each subject will be randomly assigned to receive LED-RL phototherapy at doses of 160 J/cm ² , 320 J/cm ² , or 480 J/cm ² to one side of the face, with the contralateral side receiving mock treatment.
Study Duration:	24 months
Participant	6 months

Duration:

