2 INTRODUCTION

2.1 STUDY RATIONALE

The goal of this study is to evaluate the safety and clinical efficacy of LED-RL as a treatment modality to reduce skin scarring after mini-facelift surgery. We hypothesize that LED-RL phototherapy has the potential to mitigate skin fibrosis by modulating key cellular and molecular mechanisms of fibrosis, including fibroblast proliferation and collagen formation.

Skin fibrosis is a common complication in the wound healing process and remains a challenge in clinical medicine. Clinical research on post-surgical scarring indicates that early intervention on new wounds (i.e., in the immediate post-operative period) is more beneficial than treatment of mature scars, as prevention of scar formation is the key to avoidance of poor scarring.² Despite high demand for early intervention to minimize scarring, there are few effective and durable treatments available. Skin fibrosis secondary to surgery and other trauma is due to abnormal wound healing, wherein fibroblasts remain pathologically active and continue to proliferate and produce collagen, resulting in hypertrophic scars and keloids. According to our *in vitro* data, LED-RL at fluences above 320 J/cm² demonstrates anti-fibrotic properties, limiting fibroblast proliferation and collagen deposition in the dermis.^{3,4} Furthermore, in two Phase I clinical trials, we demonstrated the safety and tolerability of LED-RL at fluences up to 480 J/cm² on normal human skin (unpublished data).

We propose to conduct a randomized split-face study to test the anti-fibrotic effects of LED-RL phototherapy in subjects who have decided to undergo elective mini-facelift surgery, using the periauricular skin incisions as the treatment sites. We chose this surgical wound model given that periauricular skin is at increased risk of scarring, yet is inconspicuous and a split-face study design allows subjects to serve as their own controls.

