The treatment side (right face versus left face) will also be randomized to control for effects of uneven sun exposure. The untreated side will receive mock therapy with sham irradiation via a mock device that looks, sounds, and feels similar to the treatment device, but does not produce light. Subjects will

be blinded to the LED-RL device versus mock device as the treatment site is outside of their range of view and they will wear safety goggles.

Beginning scar reduction therapy at 1 week after surgery (defined as POD 4 to POD 8) is a validated intervention time point for limiting surgical scars.¹ Subjects will receive their treatment sessions inoffice three times weekly, a standard phototherapy regimen,^{73–75} starting at 1 week post-surgery for a total of nine treatment sessions. This treatment schedule (frequency and duration) is identical to the schedules used in our Phase I studies. Each treatment session will be observed by an investigator to monitor for any adverse events and to ensure safety and adherence.

During the study, subjects will be asked to avoid scar treatments to both periauricular incision sites. Scar treatment options include, but are not limited to, silicone gels/sheets, intralesional corticosteroids, 5-fluorouracil, laser therapy, radiotherapy, cryotherapy, bleomycin, mitomycin C, imiquimod, pressure therapy, adhesive microporous hypoallergenic paper tape, onion extract, massage therapy, over-the-counter topical emollients for scars, laser therapy, and surgical revision.⁷⁶ As described above, subjects will be counseled on proper wound care during the postoperative period to facilitate appropriate wound healing. Refer to *Section 10.2: Additional Considerations* for a discussion of available scar treatments at the conclusion of the study.

Following the study intervention period, subjects will have follow-up assessments on approximately POD 30, 90, and 180. At each follow-up visit, scar characteristics will be recorded objectively and subjectively through skin elasticity and induration measurements, tissue histology, photographic evaluation, skin imaging analysis, collagen and water concentration measurements, OCT, and standardized patient and observer assessments as described in *Section 3: Objectives and Endpoints* and *Section 8: Study Assessments and Procedures*.

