6.2 PREPARATION/HANDLING/STORAGE/ACCOUNTABILITY

6.2.1 ACQUISITION AND ACCOUNTABILITY

The study intervention and control products were originally purchased from Photo Therapeutics. There is no distribution plan as the treatment and mock devices are already in the possession of the research team (previously purchased for the Phase I studies). Disposal of unused product is not applicable to this protocol.

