6.2.2 FORMULATION, APPEARANCE, PACKAGING, AND LABELING

The LED light source is the Omnilux new-U (GlobalMed Technologies, Glen Ellen, CA) handheld LED phototherapy device, which is commercially available and FDA cleared for treatment of periorbital wrinkles. The device contains an array of LEDs with a transparent lens cover, a ventilation fan, a three-position switch, and a connection socket. The LED has a 4.7 cm x 6.1 cm rectangular aperture and emits visible red light (633 nm \pm 6 nm) at a power density of 360.2 W/m² at room temperature.

The mock therapy device has a ventilation fan and functional resistors designed to sound, look, and feel similar to the phototherapy treatment device, but emits no irradiation.

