6.4 STUDY INTERVENTION COMPLIANCE

Subjects will be closely monitored during each treatment session to ensure appropriate dosing of the phototherapy device (as determined by length of treatment time) and subject's adherence to the protocol (i.e., the subject remains with both treatment and mock-treatment devices in the correct position). The exact start time and end time of each treatment session will be recorded in the case report forms.

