9.4.2 ANALYSIS OF THE PRIMARY EFFICACY ENDPOINT(S)

The two principal outcomes (scar pliability measurements of skin elasticity and skin induration) will be used separately as dependent variables (DVs) in mixed linear models. Fixed factors in each model will be treatment group, whether treated, side of face (left versus right), and time (3 points post-baseline). Baseline DV measure will be introduced as a scored covariate; subject ID as a random factor. The Akaike information criterion will be used to assess what intra-subject covariance structure might be optimal. Tests of Interaction among fixed factors will be conducted, and the utility of polynomial terms in the baseline DV investigated. Model residuals will be examined for skew and for outliers; the DV will be power-transformed if necessary to maximize normality of residuals.

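### The stated device irradiance, session times and fluence labels disagree by a factor of 2.47 in every arm, and the documents do not show which is wrong

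*Combined protocol and SAP*

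**What the plan says.** Section 6.1.2 fixes a session length for each arm: "Group 1: LED-RL 160 J/cm² and mock therapy 30 minutes", then 60 minutes for 320 J/cm² and 90 minutes for 480 J/cm². A subject's dose stays the same at all nine sessions, and the device sits no more than 1 cm from the skin.

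Section 6.2.2 says the device emits red light "at a power density of 360.2 W/m² at room temperature". The synopsis (Section 1.1) gives the same value.

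Section 6.4 ties dose to the clock. Sessions are monitored to ensure "appropriate dosing of the phototherapy device (as determined by length of treatment time", along with correct device position, and start and end times go on the case report form.

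The fluence scale is anchored outside the trial:
- Section 2.1 relies on laboratory work: "LED-RL at fluences above 320 J/cm² demonstrates anti-fibrotic properties".
- Sections 4.1 and 4.3 take 160 J/cm² from maximum doses in published clinical studies.
- The same sections take 480 J/cm² from the Phase I maximum tolerated dose (MTD). Section 4.3 adds a Phase I MTD of 320 J/cm² for darker skin.

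On the link to Phase I, Section 4.1 states: "This treatment schedule (frequency and duration) is identical to the schedules used in our Phase I studies". Section 6.2.1 says the devices were "previously purchased for the Phase I studies".

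The documents give no second irradiance, no measured output at skin level, no conversion factor and no check of device output.

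**The concern.** The three printed quantities are bound by one identity, fluence = irradiance × time, and they do not satisfy it. In a dose-ranging trial the J/cm² figure is what names each arm and links it to outside evidence.

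The consequence depends on which figure is wrong:
- **Irradiance and times right.** The arms receive far less than labelled. If the in vitro fluences were measured on a comparable scale, even the top arm lies below the 320 J/cm² threshold. A null result would then be reported as failure at 480 J/cm². Section 10.2 rejects a two-arm design precisely because dropping the 480 J/cm² arm might miss an effect not seen at 320.
- **Labels and times right.** The printed device specification is wrong, and the regimen cannot be reproduced from it.

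There is also a safety side. Sections 4.3 and 10.2 accept a possibly higher blister risk in subjects with skin of color in order to study 480 J/cm². That judgement should rest on a verified exposure.

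**Working it through.** **Inputs**
- Irradiance: 360.2 W/m² (Sections 1.1 and 6.2.2). Divided by 10,000 cm² per m², this is 0.03602 W/cm².
- Session times: 30, 60 and 90 min, or 1800, 3600 and 5400 s (Section 6.1.2).
- Labels: 160, 320 and 480 J/cm² (Section 6.1.2).
- Aperture: 4.7 × 6.1 = 28.67 cm² (Section 6.2.2).
- Sessions: 9 (Section 6.1.2).

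**Can the labels be reproduced?** Fluence = 0.03602 W/cm² × seconds.

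| Arm | Calculation | Delivered per session (J/cm²) | Label (J/cm²) | Label ÷ delivered |
|---|---|---|---|---|
| 1 | 0.03602 × 1800 | 64.8 | 160 | 2.468 |
| 2 | 0.03602 × 3600 | 129.7 | 320 | 2.468 |
| 3 | 0.03602 × 5400 | 194.5 | 480 | 2.468 |

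They cannot. Rounding of the irradiance (360.15 to 360.25 W/m²) moves the ratio only between 2.467 and 2.468.

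**Other readings tried**
- Sum over nine sessions: 583.5, 1167.0 and 1750.6 J/cm².
- Sum over one week (three sessions): 194.5, 389.0 and 583.5 J/cm².
- Total energy over the aperture (fluence × 28.67 cm²): 1859, 3718 and 5577 J.
- 360.2 read as mW/cm²: 0.3602 × 1800 = 648.4 J/cm² for the 30-minute arm.

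None gives 160, 320 and 480.

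**What each single correction would imply**
- Irradiance and times right: the labels become 64.8, 129.7 and 194.5 J/cm².
- Irradiance and labels right: time = label ÷ 0.03602, which is 74.0, 148.1 and 222.1 min.
- Times and labels right: irradiance = 160/1800 = 320/3600 = 480/5400 = 0.0889 W/cm², or about 889 W/m².

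Because labels and times both scale 1:2:3, a single irradiance of about 889 W/m² would reconcile all three arms. That pattern fits a misprinted or differently measured irradiance, but no passage establishes it.

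**Risk of a wrong correction.** Suppose true output is 889 W/m² and sessions are lengthened to 74, 148 and 222 min to match the printed irradiance. Delivered fluence is then label × 2.468 = 394.8, 789.7 and 1184.5 J/cm². The top arm would be at 1184.5/480 = 2.47 times the MTD.

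**The case against.** The best defence accepts the mismatch and disputes its weight.

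- **The inference is untouched.** The regimen is defined in practice by a named device, a maximum distance and fixed minutes. Section 9.4.2 enters dose only as a category: "Fixed factors in each model will be treatment group, whether treated, side of face". Randomisation and sample size do not use absolute fluence, and arms could be relabelled later from recorded times. All of this stands. The fault lies in the dose specification, not in the primary model.
- **The Phase I bridge may hold.** The devices are the same. If Phase I used the same minutes per label, tolerability carries over whatever the true output. This is possible but unproven, since the statement about frequency and duration does not say that it covers minutes per session. It would not repair the link to the in vitro or published clinical doses.
- **The efficacy consequence rests on unseen dosimetry.** That is correct, so it is stated here only conditionally.
- **The 360.2 W/m² figure has no stated measuring distance or method.** It may not be irradiance at the skin. This is a fair caveat, but the documents offer no other figure and nothing to show that measuring conditions account for a factor of 2.47.
- **A calibration step may sit in procedures not supplied.** Sections 10.1.8 and 10.1.10 mention SOPs and a manual of procedures. The supportable statement is that these documents describe no output check.
- **The lengthened-session overdose is not planned.** True. At the stated times no single-figure correction puts any arm above 480 J/cm². The scenario is only a warning about how to correct the error.

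**Conclusion.** The concern holds, with high confidence. At the printed irradiance and times the arms deliver 64.8, 129.7 and 194.5 J/cm² per session against labels of 160, 320 and 480. The common factor is 2.47 (delivered ÷ label = 0.405). The only assumption behind the calculation is that 360.2 W/m² is the irradiance reaching the skin.

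Which of the three quantities is wrong cannot be settled from the documents. That the top arm falls below the in vitro threshold requires two further conditions: that the irradiance and times are the correct figures, and that the in vitro fluences are on a comparable scale.

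This must be fixed before treatment starts, because the figure that defines each arm contradicts the protocol's only device specification.

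**What to change.** 1. Before treatment, measure the output of the study devices at the treatment distance (at most 1 cm).
2. Confirm the device output and session minutes actually used in Phase I. Do not lengthen sessions to fit the labels until this is done.
3. Correct whichever of irradiance, times or labels is wrong, so that Sections 1.1, 6.1.2 and 6.2.2 multiply consistently. Report the verified nominal fluence for each arm, and restate the comparison with the in vitro, published clinical and Phase I doses on that scale.
4. Keep randomised treatment group as the factor in the primary intention-to-treat model. Use individual delivered fluence (verified irradiance × recorded start-to-end time) only descriptively or in a supplementary analysis.

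The cost is one output check of devices the team already holds, plus a protocol text correction. It needs no extra patients and no change to the primary model. Session times are already captured on the case report form, so arms can be relabelled if necessary.
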